 - This study uses iron incorporation into erythrocytes in order to assess oral iron absorption. While it is appreciated that changes in erythrocyte iron content can be due to many factors, erythrocyte iron content is a well-recognized surrogate for iron absorption ([IAEA Human Health Series No. 21, 2012](#)). Additionally, fractional iron absorption as an endpoint allows for comparison to studies in non-anemic participants.
 - At present, three methodologies are primarily recognized for assessing fractional iron absorption: fecal recovery of the ingested isotope, plasma appearance of the ingested isotope and iron incorporation into erythrocytes following oral ingestion. Of the three, the most frequently used approach is iron incorporation into erythrocytes using single or multiple oral labels as it is more sensitive than either the fecal recovery or plasma appearance methods ([IAEA Human Health Series No. 21, 2012](#)). The majority (80%) of the iron that is absorbed is incorporated into red blood cells in Hgb, a process which occurs over 10 to 12 days. Once incorporated, the iron is stable for the lifespan of the red blood cell, a period of up to 120 days in non-anemic participants and approximately 70 days in individuals with chronic kidney disease.
 - Iron absorbed from the diet is obtained from animal-based sources, and is known as heme iron, while plant-based iron is non-heme iron. This study will assess the

absorption of non-heme iron as most of the understanding of iron absorption is related to non-heme iron which typically comprises the majority of dietary and supplemental iron.

- ND-CKD patients which have elevated levels of C-reactive protein (CRP) and hepcidin typically experience poor intestinal iron absorption ([Macdougall, 2014](#)). Therefore, hsCRP will be assessed at screening for eligibility in order to minimize the recruitment of participants with poor intestinal iron absorption due to inflammation.
- Finally, stable isotopic iron will be administered in the fasted state as the fraction of iron absorbed in the fasted state is typically much higher than that which occurs when a component of a mixed meal. A recent publication using this methodology in 18 healthy, adult female participants reported an average absorption \pm SD of $14.71 \pm 10.7\%$ in the fasted state compared to $3.63 \pm 6.5\%$ in the fed state ([Young, 2009](#)). In this regard, it is considered that a 30% change in oral iron absorption is clinically relevant.

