10.2. Sample Size Determination

Sufficient participants will be enrolled such that at least 12 participants comprise the Evaluable Population (See Section 10.3.1.3).

A sample size of 12 participants provides 90% power to detect a paired mean difference of 11% between the two treatment groups under an assumed between-participant standard deviation (SD) of 10.7%. Note this is a conservative estimate of the SD of the paired differences as it is based on a parallel design study (Young, 2009).

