10.2.1. Sample Size Sensitivity

Table 5 illustrates the impact on power for the primary efficacy analysis based on alternative assumptions for the between participant SD and the expected difference between the treatment groups.

Table 5 Impact on power based on alternative assumptions for the between participant SD and the expected difference between the treatment groups

Between participant SD (%)	Expected difference between treatments in Fractional Iron Absorption (%) (daprodustat – rhEPO (i.e., epoetin alfa or darbepoetin alfa))				
	7	9	11	13	15
7	88%	98%	>99%	>99%	>99%
9	69%	88%	97%	>99%	>99%
10.7	54%	76%	90%	97%	>99%
12	43%	66%	82%	93%	98%
14	35%	53%	70%	83%	92%

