4.2.2. Main analytical approach

Endpoint / Variables

 Fractional oral iron absorption (%)
Model Specification

 To compare daprodustat to rhEPO on fractional iron absorption, a mixed effects model will be fitted Terms fitted in the mixed effect model will include:

Endpoint / Variables

 • Fixed effect: treatment, period, and iron isotope • Random effect: participant • The Kenward and Roger method for approximating the denominator degrees of freedom and correcting for bias in the estimated variance-covariance of the fixed effects will be used. • Using PROC MIXED in SAS, the covariance for the random participant effect (G matrix) will be fit using an unstructured covariance structure by specifying ‘type=UN’ on the RANDOM line. 
 • In the event that this model fails to converge, alternative covariance structures may be considered such as Variance Components or Compound Symmetry. • Akaike’s Information Criteria (AIC) will be used to assist with the selection of covariance structure.
Model Checking & Diagnostics

 • For the Mixed Model, model assumptions will be checked, and appropriate adjustments may be applied based on the data. • Distributional assumptions underlying the model used for analysis will be examined by obtaining a normal probability plot of the residuals and a plot of the residuals versus the fitted values (i.e. checking the normality assumption and constant variance assumption of the model respectively) to gain confidence that the model assumptions are reasonable. • If there are any departures from the distributional assumptions, alternative transformations, such as data squared or square root of data, will be explored. • Non-parametric analyses will be conducted if the normality assumption does not hold.
Model Results Presentation

Fractional oral iron absorption will be summarized using n, mean, SD, median, minimum, and maximum.
 
Point estimates, corresponding 95% confidence intervals, and two-sided p-values will be constructed for the comparison of efficacy of daprodustat to rhEPO.

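### The SD of 10.7 is called a conservative SD of paired differences without support, and Table 5 gives the SD it uses the wrong name

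*Protocol*

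**What the plan says.** Protocol 10.2 plans for at least 12 evaluable participants. It states 90% power for a paired mean difference of 11 percentage points "under an assumed between-participant standard deviation (SD) of 10.7"%. The next sentence gives that figure its role in the calculation: "Note this is a conservative estimate of the SD of the paired differences as it is based on a parallel design study". SAP 5 repeats both statements. No other reason is offered.

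The origin of 10.7 is in Protocol 5.4: "A recent publication using this methodology in 18 healthy, adult female participants reported an average absorption" of 14.71% with an SD of 10.7% in the fasted state. It is therefore the SD of one measurement per person, in healthy women.

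Protocol 10.2.1 then tabulates power for five SDs and five differences. The title of Table 5 reads "Impact on power based on alternative assumptions for the between participant SD", and the lead-in sentence and row header use the same name for the SD.

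**The concern.** In a crossover, the precision of the treatment comparison depends on the SD of within-participant differences. A parallel study supplies the SD of single values. The two are linked by the correlation between a participant's two measurements, and a parallel study does not show that correlation. The design of the source is therefore no reason to expect 10.7 to be too large rather than too small.

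The SD is also named in two ways. The power sentence and Table 5 call it a between-participant SD, while the explanatory sentence treats it as the SD of paired differences. A reader who takes a between-participant SD from another study and looks it up in Table 5 will in general read off the wrong power.

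What is at stake is how the planning claim is read. This is the only variance justification for the target of 12, and Protocol 10.2.2 rules out re-estimation of the sample size. After a null result, a power of 90% on an SD described as conservative would claim more than the documents establish.

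**Working it through.** **Inputs.** n = 12, difference 11 and SD 10.7 come from Protocol 10.2. The sample-size section gives no significance level. Two-sided 5% is inferred from the 95% confidence intervals and two-sided p-values in SAP 4.2.2, and it reproduces the stated power.

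**1. The plan's own figure.** Enter 10.7 as the SD of paired differences in a paired t-test with 11 df:

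- noncentrality = 11 / (10.7/√12) = 3.56
- power from the noncentral t distribution = 89.9%, against 90% stated.

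The alternatives tried do not give 90%: the paired normal approximation gives 94.5%, and a two-sample t-test with 12 per arm gives 67.3%. So 10.7 was used as the SD of differences.

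**2. From single values to differences.** If single values have SD s under both treatments and correlation ρ, then SD_diff = s × √(2(1 − ρ)). Taking s = 10.7 under both treatments (an assumption):

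| ρ | SD_diff | Power for 11 points, 11 df |
|---|---|---|
| 0 | 15.13 | 63% |
| 0.3 | 12.66 | 78% |
| 0.4 | 11.72 | 84% |
| 0.5 | 10.70 | 90% |
| 0.6 | 9.57 | 95% |

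The value 10.7 is conservative only for ρ above 0.5.

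**3. The threshold depends on s.** Setting SD_diff = 10.7 gives ρ = 1 − (10.7/s)²/2. This is 0.11 for s = 8, 0.29 for 9, 0.43 for 10, 0.50 for 10.7, 0.60 for 12 and 0.71 for 14. For s up to 10.7/√2 = 7.57, any ρ of 0 or above is enough. With unequal SDs, ρ = (s₁² + s₂² − 10.7²)/(2s₁s₂), which is 0.37 for 10.7 and 8, and 0.61 for 10.7 and 13. Neither document states a correlation, an SD of differences or an SD of absorption in CKD patients.

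**4. Table 5.** With each row value entered as the SD of paired differences on 11 df, 24 of the 25 cells match to rounding. The exception is SD 12 with difference 7: printed 43%, recomputed 45.4%. If the 10.7 row were read literally as a single-value SD with ρ = 0, it would show 31, 47, 63, 77 and 88%. The printed row is 54, 76, 90, 97 and >99%. With a common SD under both treatments, label and entries agree only at ρ = 0.5.

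**5. Degrees of freedom (side point).** SAP 4.2.2 lists "Fixed effect: treatment, period, and iron isotope". With exactly 12 evaluable participants, three per sequence, the 12 period differences support three parameters (period, treatment, isotope), leaving 12 − 3 = 9 df. The treatment contrast is orthogonal to the other two, so its variance is still SD_diff²/12. Power at the design point becomes 88.5%.

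**The case against.** The best defence is that each participant serves as their own control, so a positive correlation is expected, and that the plan openly says it substitutes one SD for the other. Table 5 also already covers larger SDs: at 11 points, 82% for SD 12 and 70% for SD 14. With s = 10.7, SD 14 corresponds to ρ = 1 − (14/10.7)²/2 ≈ 0.14, so the table covers nearly the whole range of non-negative correlations. The 63% at ρ = 0 is a corner case.

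Variability in this trial could also be lower than in the source. Protocol 5.4 reports an SD of 6.5 for the fed state at a lower mean. With s = 6.5, SD_diff is only 6.5 × √2 = 9.2 even at ρ = 0. This is suggestive only, because the isotope is given fasted. The same section says "ND-CKD patients which have elevated levels of C-reactive protein (CRP) and hepcidin typically experience poor intestinal iron absorption". That sentence concerns the level of absorption, not its spread, and the section adds that hsCRP screening is meant to limit recruitment of such patients. It does not settle the SD in either direction.

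Much of this stands. The arithmetic of the 90% is right, the substitution is disclosed, and sensitivity to a larger SD is shown. What remains is that a positive correlation is not enough at s = 10.7: it must exceed 0.5, and the documents give no value. The row label can be called loose rather than wrong, since differences also vary between participants. But Protocol 10.2 itself uses the between-participant name for a figure that is an SD of single values.

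A reader might infer that the trial is underpowered or needs more participants. The documents do not support that, because a correlation above 0.5 or a smaller SD in this population is entirely possible.

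**Conclusion.** The concern holds as a fault of justification and labelling. A parallel source does not make 10.7 a conservative SD of paired differences. With a single-value SD of 10.7 under both treatments, that needs a correlation above 0.5; the threshold is lower if participants in this trial vary less and higher if they vary more. Under the same assumption, power for 11 points runs from 63% at correlation 0 to 95% at 0.6, so the stated 90% may be too high or too low.

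The 90% is correct for the SD entered, and underpowering is not shown. The Table 5 powers are right for an SD of paired differences, apart from one cell that is about 2 points too low. The planned analysis and its confidence interval are not affected. The correction is worth making because it is cheap and concerns the only support given for the sample size.

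**What to change.** 1. In Protocol 10.2 and SAP 5, name the 10.7 as the SD of paired differences in the power sentence. Replace the sentence claiming conservatism with: *The 90% assumes an SD of paired differences of 10.7, which corresponds to a within-participant correlation of 0.5 if the SD of a single measurement is 10.7 under both treatments; no estimate of either for this population is cited.*
2. In Table 5 (title, lead-in sentence and row header), replace "between participant SD" with *SD of paired differences*. State that the powers are for a paired t-test with 11 df, and correct SD 12, difference 7 from 43% to 45%.
3. Optional: add a row for SD 15.1 (31, 47, 63, 77 and 88% for differences 7, 9, 11, 13 and 15) as the zero-correlation case. Add a note that with exactly 12 evaluable participants the planned model has 9 df and gives 88.5% at the design point.

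The cost is wording in two sections and edits to one table. Enrolment and analysis stay as they are; the plan gives up only the description of its SD as conservative.

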10.2.1. Sample Size Sensitivity

Table 5 illustrates the impact on power for the primary efficacy analysis based on alternative assumptions for the between participant SD and the expected difference between the treatment groups.

Table 5 Impact on power based on alternative assumptions for the between participant SD and the expected difference between the treatment groups

Between participant SD (%)	Expected difference between treatments in Fractional Iron Absorption (%) (daprodustat – rhEPO (i.e., epoetin alfa or darbepoetin alfa))				
	7	9	11	13	15
7	88%	98%	>99%	>99%	>99%
9	69%	88%	97%	>99%	>99%
10.7	54%	76%	90%	97%	>99%
12	43%	66%	82%	93%	98%
14	35%	53%	70%	83%	92%

10.2.2. Sample Size Re-estimation

No sample size re-estimation will be performed.

10.3. Data Analysis Considerations

10.3.1. Analysis Populations

10.3.1.1. Screened Population:

This population consists of all participants who signed an ICF to participate in the clinical trial. This population will be used for summarizing screening failure rates and reasons for screening failure.

10.3.1.2. Safety Population:

This population consists of all randomized participants who received at least one dose of study treatment. This will be the primary population for the safety analyses.

10.3.1.3. Evaluable Population:

This population consists of all randomized participants who received study medication and completed the iron absorption assessment for both treatment periods. This population will be used for the primary endpoint analysis.

10.3.1.4. Modified Intent to Treat (mITT) Population:

This population consists of all randomized participants who received study medication and completed the iron absorption assessment at the end of the first treatment period. This population will be used for the sensitivity analysis of the primary endpoint.

10.3.2. Interim Analyses

No interim analysis will be performed for this study.

10.4. Key Elements of Analysis Plan

10.4.1. Primary Analysis

To compare daprodustat to rhEPO (i.e., epoetin alfa or darbepoetin alfa) on fractional iron absorption, a mixed effect model will be fitted with fixed effect terms for treatment, sequence, period and iron isotope and a random effect for participant-within-sequence. The term sequence will consist of the four combinations of treatment and iron isotope assignments. Point estimates and corresponding 95% confidence intervals will be constructed for the comparison of efficacy of daprodustat to rhEPO.

A sensitivity analysis for this primary analysis will be performed using the same mixed modeling approach, except with the mITT population.

Descriptive statistics (n, arithmetic mean, standard deviation, 95% CI, minimum, median and maximum) will be calculated for fractional iron absorption (%) at the Day 29 and Day 57 visits.

10.4.2. Secondary Analysis

Descriptive statistics (n, arithmetic mean, standard deviation, 95% CI, minimum, median and maximum) will be calculated for iron markers and indices of erythropoiesis at each scheduled visit.

Safety data will be presented in tabular and/or graphical format and summarized descriptively according to GSK's Integrated Data Standards Library (IDSL) standards.

Further details will be given in the Reporting Analysis Plan (RAP).

12. APPENDICES

12.1. Appendix 1: Abbreviations and Trademarks

Table 6 List of Abbreviations

Ab	Antibody
AE	Adverse event
AESI	Adverse events of special interest
ALT	Alanine aminotransferase (SGPT)
AST	Aspartate aminotransferase (SGOT)
AUC	Area under the concentration-time curve
BCRP	Breast Cancer Resistance Protein
BUN	Blood urea nitrogen
CI	Confidence Interval
CKD	Chronic kidney disease
CKD-EPI	Chronic kidney disease Epidemiology Collaboration
CIOMS	Council for International Organizations of Medical Sciences
C _{max}	Maximum observed concentration
CPK	Creatine phosphokinase
CONSORT	Consolidated Standards of Reporting Trials
CRF	Case Report Form
hsCRP	High sensitivity C-reactive protein
CV	Cardiovascular
CYP	Cytochrome P450 enzyme
DcytB	Duodenal cytochrome b561
dL	deciliter
DMT1	Divalent metal-iron transporter 1
DNA	Deoxyribonucleic acid
ECG	Electrocardiogram
eCRF	Electronic Case Report Form
eGFR	Estimated glomerular filtration rate
EPO	Erythropoietin
ESA	Erythropoiesis-stimulating agent
FDA	Food and Drug Administration
Fe	Iron
FPN	Ferroportin
FSH	Follicle stimulating hormone
g	Gram
GCP	Good Clinical Practice
GDF15	Growth differentiation factor 15
GI	Gastrointestinal
GSK	GlaxoSmithKline
HBsAg	Hepatitis B surface antigen
hCG	Human chorionic gonadotropin
HD	Hemodialysis dependent
Hgb	Hgb
HIF	Hypoxia-inducible factor
HIV	Human Immunodeficiency Virus
HIPAA	Health Insurance Portability and Accountability Act

HPLC	High performance liquid chromatography
HRE	Hypoxia response element
IAEA	International Atomic Energy Agency
IB	Investigator's Brochure
IC ₅₀	Half maximal inhibitory concentration
ICH	International Conference on Harmonization of Technical Requirements for Registration of Pharmaceuticals for Human Use
ICF	Informed Consent Form
IEC	Independent ethics committee
IgG	Immunoglobulin G
IgM	Immunoglobulin M
IND	Investigational new drug
INR	International normalization ratio
IRB	Institutional Review Board
IU	International units
IUD	Intrauterine device
IUS	Intrauterine system
IV	Intravenous
KDOQI	Kidney Disease Outcomes Quality Initiative
Kg	Kilogram
LDH	Lactate dehydrogenase
LVEF	Left ventricular ejection fraction
MCH	Mean corpuscular Hgb
MCV	Mean corpuscular volume
MedDRA	Medical Dictionary for Regulatory Activities
mg	Milligrams
MI	Myocardial infarction
mL	Milliliter
mmHg	Millimeters of mercury
MSDS	Material Safety Data Sheet
msec	Milliseconds
μM	Micromolar
ng	Nanogram
ND	Nondialysis dependent
NOAEL	No observed adverse effect level
NYHA	New York Heart Association
OATP	Organic anion transporting polypeptide
PCI	Potential clinical importance
PD	Pharmacodynamic
PHD	prolyl-4-hydroxylases
PHIs	Prolyl hydroxylase inhibitors
PK	Pharmacokinetic
PRVP	Peak right ventricular pressure
PSRAE	Possible Suicidality Related Adverse Events
QTc	Corrected QT interval
QTcB	QT duration corrected for heart rate by Bazett's formula
RAP	Report and Analysis Plan
RBC	Red blood cells
rhEPO	Recombinant human erythropoietin
RNA	Ribonucleic acid

SAE	Serious Adverse Event
SD	Standard deviation
SGOT	Serum glutamic-oxaloacetic transaminase
SGPT	Serum glutamic pyruvic transaminase
SO ₄	Sulfate
SoA	Schedule of Assessments
sPAP	systolic Pulmonary Artery Pressure
SRM	Study Reference Manual
SUSAR	Suspected unexpected serious adverse reactions
TIMS	Thermal ionization mass spectrometry
TF	Transferrin
TSAT	Transferrin saturation
VEGF	Vascular endothelial growth factor
ULN	Upper limit of normal
UK	United Kingdom
US	United States
WBC	White blood cells
WOCBP	Woman of Child Bearing Potential

Trademark Information

Trademarks of the GlaxoSmithKline group of companies
NONE

Trademarks not owned by the GlaxoSmithKline group of companies
Aranesp (darbepoetin alfa)
Chiron RIBA
Epogen (epoetin alfa)
HemoCue
Procrit (epoetin alfa)
SAS
WinNonlin

12.2. Appendix 2: Liver Safety Required Actions and Follow up Assessments

Phase III-IV liver chemistry stopping criteria have been designed to assure participant safety and to evaluate liver event etiology (in alignment with the FDA premarketing clinical liver safety guidance).

<http://www.fda.gov/downloads/Drugs/GuidanceComplianceRegulatoryInformation/Guidances/UCM174090.pdf>.

Table 7 Phase III-IV liver chemistry stopping criteria and required follow-up assessments

Liver Chemistry Stopping Criteria - Liver Stopping Event	
ALT-absolute	ALT \geq 8xULN
ALT Increase	ALT \geq 5xULN but $<$ 8xULN persists for \geq 2 weeks ALT \geq 3xULN but $<$ 5xULN persists for \geq 4 weeks
Bilirubin^{1,2}	ALT \geq 3xULN and bilirubin \geq 2xULN ($>$ 35% direct bilirubin)
INR²	ALT \geq 3xULN and INR $>$ 1.5, if INR measured
Cannot Monitor	ALT \geq 5xULN but $<$ 8xULN and cannot be monitored weekly for \geq 2 weeks ALT \geq 3xULN but $<$ 5xULN and cannot be monitored weekly for \geq 4 weeks
Symptomatic³	ALT \geq 3xULN associated with symptoms (new or worsening) believed to be related to liver injury or hypersensitivity
Required Actions and Follow up Assessments following ANY Liver Stopping Event	
Actions	Follow Up Assessments

 Immediately discontinue study treatment Report the event to GSK within 24 hours Complete the liver event eCRF and complete an SAE data collection tool if the event also meets the criteria for an SAE² Perform liver event follow up assessments Monitor the participant until liver chemistries resolve, stabilize, or return to within baseline (Day 1 predose) (see MONITORING below) 	
 Viral hepatitis serology⁴ Obtain INR and recheck with each liver chemistry assessment until the transaminases values show downward trend Only in those with underlying chronic hepatitis B at study entry (identified by positive hepatitis B surface antigen) quantitative hepatitis B DNA and hepatitis delta antibody⁵.

Liver Chemistry Stopping Criteria - Liver Stopping Event	

 • Do not restart/rechallenge participant 
MONITORING:
 
For bilirubin or INR criteria:
 
 • Repeat liver chemistries (include ALT, AST, alkaline phosphatase, bilirubin) and perform liver event follow up assessments within 24 hrs • Monitor participants twice weekly until liver chemistries resolve, stabilize or return to within baseline (Day 1 predose) • A specialist or hepatology consultation is recommended 
For All other criteria:
 
 • Repeat liver chemistries (include ALT, AST, alkaline phosphatase, bilirubin) and perform liver event follow up assessments within 24-72 hrs • Monitor participants weekly until liver chemistries resolve, stabilize or return to within baseline (Day 1 predose) 	
 • Blood sample for pharmacokinetic (PK) analysis, obtained within 48 hrs after last dose⁶ • Serum creatine phosphokinase (CPK) and lactate dehydrogenase (LDH). • Fractionate bilirubin, if total bilirubin $\geq 2 \times \text{ULN}$ • Obtain complete blood count with differential to assess eosinophilia • Record the appearance or worsening of clinical symptoms of liver injury, or hypersensitivity, on the AE report form • Record use of concomitant medications on the concomitant medications report form including acetaminophen, herbal remedies, other over the counter medications. • Record alcohol use on the liver event alcohol intake case report form 
For bilirubin or INR criteria:
 
 • Anti-nuclear antibody, anti-smooth muscle antibody, Type 1 anti-liver kidney microsomal antibodies, and quantitative total immunoglobulin G (IgG or gamma globulins). • Serum acetaminophen adduct HPLC assay (quantifies potential acetaminophen contribution to liver injury in subjects with definite or likely acetaminophen use in the preceding week [James, 2009]). • Liver imaging (ultrasound, magnetic resonance, or computerised tomography) and /or liver biopsy to evaluate liver disease; complete Liver Imaging and/or Liver Biopsy CRF forms.

¹ Serum bilirubin fractionation should be performed if testing is available. If serum bilirubin fractionation is not immediately available, discontinue study treatment for that subject if ALT $\geq 3 \times \text{ULN}$ and bilirubin $\geq 2 \times \text{ULN}$. Additionally, if serum bilirubin fractionation testing is unavailable, **record presence of detectable urinary bilirubin on dipstick**, indicating direct bilirubin elevations and suggesting liver injury.

² All events of ALT $\geq 3 \times \text{ULN}$ and bilirubin $\geq 2 \times \text{ULN}$ (>35% direct bilirubin) or ALT $\geq 3 \times \text{ULN}$ and INR >1.5, if INR measured which may indicate severe liver injury (possible 'Hy's Law'), **must be reported as an SAE (excluding studies of hepatic impairment or cirrhosis)**; INR measurement is not required and the threshold value stated will not apply to subjects receiving anticoagulants

³ New or worsening symptoms believed to be related to liver injury (such as fatigue, nausea, vomiting, right upper quadrant pain or tenderness, or jaundice) or believed to be related to hypersensitivity (such as fever, rash or eosinophilia)

⁴ Includes: Hepatitis A IgM antibody; Hepatitis B surface antigen and Hepatitis B Core Antibody (IgM); Hepatitis C RNA; Cytomegalovirus IgM antibody; Epstein-Barr viral capsid antigen IgM antibody (or if unavailable, obtain heterophile antibody or monospot testing); Hepatitis E IgM antibody

⁵ If hepatitis delta antibody assay cannot be performed, it can be replaced with a PCR of hepatitis D RNA virus (where needed) [Le Gal, 2005].

⁶ PK sample may not be required for subjects known to be receiving placebo or non-GSK comparator treatments. Record the date/time of the PK blood sample draw and the date/time of the last dose of study treatment prior to blood sample draw on the CRF. If the date or time of the last dose is unclear, provide the subject's best approximation. If the date/time of the last dose cannot be approximated OR a PK sample cannot be collected in the time period indicated above, do not obtain a PK sample. Instructions for sample handling and shipping are in the SRM.

References

